4.2 Exclusion Criteria

- Age<18 years
- Known pregnancy or patients without a documented pregnancy test if not menopausal.
- Known prior anaphylactic or allergic reaction to B12a
- CKD stage 4 or worse (GFR \leq 30 ml/min) before study drug administration
- ECMO (extracorporeal membrane oxygenation) or IABP (intra-aortic balloon pump)prior to study consent and post cardiopulmonary bypass
- Patients currently on cardiopulmonary bypass
- Circumstances for which the safety of the patient could be jeopardized by continued adherence to the study protocol

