1.3 Preclinical Data

ii) Preliminary Studies

Concerns over the host of adverse effects seen with the use of MB have led to a search for other NOS inhibitors. One such medication is hydroxocobalamin also known as vitamin B12a (B12a). B12a has been used in Europe for the treatment of cyanide toxicity for over 40 years with an excellent safety profile[28]. Hypertension is one of the possible effects of B12a likely through inhibition of both NOS and cGMP [2, 10]. Given its lack of MOA-A inhibition it does not result in serotonin syndrome. Several case reports have demonstrated its effectiveness in patients with vasoplegia with one suggesting it reduced the risks of vasospasm associated with high dose

catecholamine administration and another hypothesizing a synergistic effect when used with MB [2, 12, 29].

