1.4 Clinical Data to Date

To date no prospective studies have looked at the use of B12a in this population. Currently it is FDA approved for use in cyanide toxicity with a more extensive body of literature for that indication[30].

At our institution a protocol was put in place for the use of B12a in patients with refractory VS after cardiac surgery. A retrospective review of the data sent for publication found a statistically significant increase in blood pressure and decrease in vasopressor requirement in 24 patients who received B12a in post-cardiotomy VS. This included both patients who had not received MB and patients who were B12a non-responders.

In addition a case series was recently published in the Canadian Journal of Anesthesiology also showing a favorable response in a subset of patients with post-cardiotomy VS receiving B12a [31].

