3.3 Duration of Participation

Patients will be randomized and administered study drug if criteria are met within the first 24hrs after being removed from cardiopulmonary bypass. Once study drug is given, hemodynamic variables will be monitored the first 30 minutes, all adverse events will be monitored the first 12 hours and development of acute kidney injury (AKI) and stroke will be monitored for 72 hours. Data will be collected the first 7 days through the electronic medical record and at 30 days the patient will be called for follow up and assessment of 30 day mortality.

Screening/Consent

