5. ICU LOS
6. Ventilator time (hrs)
7. Urine output (Daily for 7 days)
8. Total crystalloid and albumin administration (amount given over first 48 hrs)
9. End organ dysfunction during the first seven days will not be directly collected in the CRF but will be captured retrospectively in supportive documentation: (Stroke, AKI (AKIN criteria), Liver enzyme elevation, lactate, renal replacement therapy all daily for first seven days)
10. Maximum SOFA score (daily for first 7 days)
11. New arrhythmias (daily for first 7 days)
12. Need for Rescue with MB
13. Need for mechanical circulatory support
14. Change in INR, platelet count, fibrinogen (daily for first 7 days)
15. Need for transfusion of allogeneic packed red blood cells, plasma, platelets and fibrinogen. (Units and L transfused over first 48 hrs)
16. Compare vitamin B12 assay and heavy metal quant in patients who receive study drug

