4.1 Inclusion Criteria

- Patients/LAR will be consented prior to going to the operating room or in the intensive care unit after surgery.
- The benefits and risks will be discussed.

Table 1

Inclusion

 1. Any patient for whom we are able to obtain consent prior to their procedure or after their procedure in the intensive care unit. 2. Patient must have a PA catheter, or a CCO/Flo Trak for the procedure 3. Is presenting for a procedure in which CPB will be required 4. Is considered high risk for VS 
 a. Patient considered to be at high risk for the development of VS will be identified per the guidelines developed by Levin et al¹¹. This includes any patient: 
 I. With pre-CPB vasopressor requirement(s) or II. On pre-operative ACE, or beta-blocker or calcium channel blocker therapy or III. With a euroSCORE>6 or IV. Presenting for pericardectomy, aneurysm surgery, LVAD surgery or heart transplant, CABG or valve surgery other than a single mitral valve repair. 5. Has no contraindications to arterial line or PA catheter placement 6. Patient must fall into the defined parameters below for the majority of measurements over a 30 minute period (ex: 3 out of 5 measurements or 6 of 10, etc). 
 a. Develops high-dose vasopressors for 30 min or longer and refractory hypotension consistent with VS within 24 hours of coming off CPB. b. “high-dose vasopressor” will be defined as: 
 I. Norepinephrine infusion\geq0.1mcg/kg/min and/or II. Dopamine infusion\geq15mcg/kg/min and/or III. Epinephrine infusion\geq0.1mcg/kg/min Or c. Norepinephrine equivalent infusion of \geq 0.1mcg/kg/min (Table 1 Appendix) d. “Hypotension consistent with VS” will be defined as: 
 I. MAP\leq75 mmHg via arterial line monitor 7. Cardiac index$>$2.3L/min/m² via PA catheter monitor. 8. If at the time study drug arrives, the patient who previously met criteria has fallen out, they must once again meet requirements only one time before the drug is given.

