5.6 Prior and Concomitant Therapy

5.7 Packaging

- A full one time dose will be administered and so no drug return is expected.
- Drug will be documented by the RN, CRNA or anesthesiologist of record.

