7.1 Sample Size Determination

Sample size

Power analysis using the results of our retrospective review revealed a study population of 50 patients randomized to either B12a or control would detect a mean arterial pressure (MAP) increase of 7.3mmHg with a power of 0.8 and a p value of 0.05. The expected event rate triggering randomization is between 10% and 20% based on both historical data from previous series and evaluation of the percentage of patients meeting inclusion criteria based on a random selection of patients after cardiac surgery at our institution [5, 14]. This will require consent of 1000 to 2000 patients in order to randomize 50 patients. Our institution performs approximately 3000 cardiac surgical cases requiring CPB per year meaning we would need to consent between 4% and 8% of our cardiac surgical volume over a 2 year study period.

Problems and Limitations

Several potential limitations exist with this study. Firstly there is still no universally accepted definition of VS in the literature. Therefore physiological variables chosen for inclusion will by necessity be arbitrary. We chose variables based on definitions used in previous reviews. Furthermore, previous work suggests NOS inhibitors may be most effective early in the disease process and may be less effective after prolonged refractory VS [5, 22]. Given this we decided intervention with the study drug should occur while vasoplegia is refractory but before intervention would be considered as a rescue and therefore infusion of norepinephrine equivalents of 0.1mcg/kg/min² for 30 min was considered appropriate.

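### The entry rules admit patients already given methylene blue or non-study hydroxocobalamin before study drug, and the analysis takes no account of it

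*Combined protocol and SAP*

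**What the plan says.** **Eligibility.** A patient qualifies with high-dose vasopressors for at least 30 minutes and "refractory hypotension consistent with VS within 24 hours of coming off CPB" (section 4.1, Table 1). Section 3.3 gives the same outer limit: "Patients will be randomized and administered study drug if criteria are met within the first 24hrs after being removed from cardiopulmonary bypass". Section 4.2 refers to the study drug once, as "Known prior anaphylactic or allergic reaction to B12a". Neither list mentions earlier receipt of MB or hydroxocobalamin. Table 1 item 8 re-checks a patient who has fallen out of criteria by the time study drug arrives, but only against those same criteria.

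**Prior therapy.** Section 5.6, "Prior and Concomitant Therapy", is a heading with no text and no redaction mark in the document as supplied.

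**Intent.** Under Problems and Limitations, section 7.1 explains the vasopressor threshold by saying that "intervention with the study drug should occur while vasoplegia is refractory but before intervention would be considered as a rescue".

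**Availability of both agents.** Section 1.4 reports that at this institution "a protocol was put in place for the use of B12a in patients with refractory VS after cardiac surgery". Sections 1.2 and 5.2 let the primary team order open-label Cyanokit. Sections 1.6 and 3.1 make MB available as rescue.

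**Interaction.** The background describes both agents as acting on the nitric oxide/cGMP pathway. Section 1.3 cites case reports, with "another hypothesizing a synergistic effect when used with MB".

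**Analysis.** The primary ANCOVA adjusts for baseline MAP (section 7.2). Section 5.3 describes no stratification.

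**The concern.** A patient who received MB in the operating room or ICU, and who still has a low MAP on qualifying vasopressors, meets every written criterion. So does a patient who received hydroxocobalamin clinically.

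The second case is the sharper one. If that patient is randomized to placebo, the control arm contains someone already exposed to the active drug. If randomized to B12a, the patient is receiving a further dose. The contrast in such patients is no longer B12a against no B12a.

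A patient given MB first may be a non-responder on the shared pathway, or may be receiving a combination. Either way, the B12a effect in that patient may differ from the effect in a patient treated with neither agent.

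At stake are the power for the primary MAP comparison, the meaning of the estimate, and its sensitivity to a few patients falling unevenly between small arms.

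**Working it through.** **1. The plan's own figure.** Section 7.1 states 50 patients, a MAP increase of 7.3 mmHg, power 0.8 and p 0.05. It does not give the SD, the sidedness or the allocation ratio, so N=50 cannot be reproduced independently. The SD can only be back-solved. Assuming 25 per arm, two-sided 0.05 and the normal approximation:

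SD = 7.3 / [(1.960 + 0.842) × √(2/25)] = 7.3 / 0.792 = 9.21 mmHg.

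The t distribution gives 9.03, and a one-sided test gives 10.38. This is circular and neither confirms nor refutes the stated N. It only provides a scale. The standard error of the difference is 9.21 × √(2/25) = 2.61 mmHg.

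**2. Effect on the contrast.** Let f be the fraction pre-treated and k the share of the 7.3 mmHg effect that remains in them. The documents give neither.

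Average effect = 7.3 × (1 − f + f·k). Power = Φ(effect / 2.61 − 1.960).

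With no remaining effect (k = 0):

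| f | Effect (mmHg) | Power | Total N for 0.80 |
|---|---|---|---|
| 0% | 7.3 | 0.80 | 50 |
| 5% | 6.9 | 0.76 | 56 |
| 10% | 6.6 | 0.71 | 62 |
| 20% | 5.8 | 0.61 | 80 |
| 30% | 5.1 | 0.50 | 104 |

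If half the effect remains (k = 0.5), power is 0.78, 0.76, 0.71 and 0.66 at f = 5%, 10%, 20% and 30%.

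Synergy would work the other way. With k = 1.5, chosen only to show the direction, f = 20% gives 7.3 × 1.10 = 8.03 mmHg and power 0.87. These figures hold the SD fixed and ignore the extra variance from mixing patients with different effects.

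**3. Chance imbalance.** Take the number of pre-treated patients in each arm as independent binomials with n = 25. The probability that the arms differ by four or more (4/25 = 16 percentage points) is about 10% at 10% prevalence, 21% at 20% and 28% at 30%.

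**4. Is exposure related to the arm?** Exposure before randomization is balanced in expectation. Table 1 item 8 implies a short interval between randomization by the pharmacy and arrival of the drug. Anything given then still precedes the blinded dose, so it cannot depend on the arm while allocation is concealed.

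**5. What is recorded.** Section 6 schedules history and concurrent medications on Day 0 and Day 1, so earlier exposure should be recoverable. It is not a named data item in section 3.7, and no analysis in section 7.2 uses it.

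**The case against.** The best defence is that this is a legitimate mixed population. The primary objective and hypothesis name vasoplegic patients on high-dose vasopressors, not patients untreated with MB or B12a. The pre-rescue sentence in section 7.1 is a rationale for the threshold, and the threshold is how the intent was put into practice. It makes earlier rescue less likely, and the 24-hour limit caps the interval. Section 1.4 describes the institutional B12a protocol in the past tense, as the source of a retrospective series. That series appears to have been mixed on MB exposure, although its wording is unclear, so 7.3 mmHg may already reflect some prior MB.

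Much of this stands. The plan may choose a mixed population, but it should then say so, and an empty section 5.6 does not. A threshold that makes prior rescue less likely does not prevent it. The mixed-series argument bears on MB. It does not defend admitting to the placebo arm a patient who has already had the active drug.

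Three stronger readings are tempting and are not supported:

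- *MB given before dosing would be counted as a rescue outcome.* The listed outcome, "Need for Rescue with MB" (section 3.5), has no start time. However, sections 1.6 and 3.1 place MB rescue after non-response to study drug or placebo, and section 3.1 says that this use is what is measured.
- *Consent sought after surgery makes pre-treatment more likely.* Section 4.3 approaches patients who are close to qualifying, which means they have not yet met the thresholds. The documents do not show that such patients are more often pre-treated.
- *The treatment comparison is biased.* Step 4 of the working shows why it is not.

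**Conclusion.** The gap is real: three places where a limit on prior same-pathway treatment could stand (Table 1, section 4.2 and section 5.6) contain none, and they do not carry through the intent stated in section 7.1. The consequence is possible dilution or alteration of the effect, added variance and chance imbalance.

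The fall in power to about 0.71 or 0.61 is an illustration, not an estimate of what this trial will lose. It rests on 1:1 allocation, a two-sided test, the back-solved SD, assumed pre-treatment rates of 10% and 20%, and complete loss of effect in pre-treated patients. If few patients are pre-treated, the effect on power is small; under synergy it could reverse.

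The change is worth making because it is cheap and protects the meaning of the control arm. The figure in section 3.1 is not shown in the supplied text and was not relied on.

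**What to change.** - Reconcile sections 4.1, 4.2 and 5.6 with section 7.1. Complete section 5.6 so that it states whether prior MB and prior non-study hydroxocobalamin are allowed.
- Add to section 4.2 an exclusion for non-study hydroxocobalamin given between the start of the index surgery and T0, re-checked when study drug arrives. That re-check appears to fall after randomization, so state how a patient who fails it is counted. Under section 7.3 such a patient remains in the all-randomized population.
- For prior MB, choose one of two routes: exclude it in the same way, or record it with its time on the CRF and pre-specify a sensitivity analysis without those patients.
- As a clarification only, state that MB rescue means first MB use after T0, as section 3.1 already implies.

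These are rules on entry and analysis. They do not change what the treating team may give.

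**Cost.** A few lines of text and one check of the medication record. Some otherwise eligible patients may be lost, and the number depends on the same unknown rate. To randomize 50, about 50/0.9 = 56 patients would have to meet the other criteria at 10% pre-treated, and 50/0.8 = 62.5, so 63, at 20%.

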4.3 Subject Recruitment, Enrollment and Screening

Study coordinators will screen all adult (age > 18) patients who are scheduled to undergo coronary artery bypass graft surgery with or without valve repair/replacement, complex cardiac valve surgery, pericardial resection, and/or ascending aortic surgery at Mayo Clinic Rochester. Eligible patients will be approached by a study coordinator for consent before their elective surgical procedure or patient/LAR will be approached after the surgical procedure in the intensive care unit if the patient is close to qualifying for the study. After confirming the patient's inclusion and exclusion criteria, the study coordinator at the institution will obtain informed consent and assign a study ID number to the study participant. Screening logs will be maintained to allow generation of a CONSORT diagram.

4.4 Early Withdrawal of Subjects

- We expect early withdrawals to be rare given it is a single intervention.
- Patients will be free to withdraw consent at any time during the study period.
- Patients who withdraw will be included in intention to treat analysis and safety assessment and analysis.

4.4.1 When and How to Withdraw Subjects

- Patient/LAR will be able to withdraw consent at any time if the patient no longer wishes to participate.

5 Study Drug

5.1 Description

- The study drug, hydroxocobalamin is marketed as Cyanokit® and comes in a 200ml glass vial as a red powder which is reconstituted in 200ml of normal saline giving a dark red solution.

5.2 Treatment Regimen

- 5g, IV, over 15 min as a single dose. Can order unblinded dose of Cyanokit® within the first 4 hours at the discretion of the primary care team.

5.3 Method for Assigning Subjects to Treatment Groups

- Patients will be randomized by research pharmacy if they meet inclusion criteria.

5.4 Preparation and Administration of Study Drug

- Both the study drug and placebo will be randomized by the research pharmacy.

5.5 Subject Compliance Monitoring

- Patient non-compliance is not expected to occur as the patient will be intubated and ventilated and it is a single dose IV medication administered by OR and ICU staff.

5.6 Prior and Concomitant Therapy

5.7 Packaging

- A full one time dose will be administered and so no drug return is expected.
- Drug will be documented by the RN, CRNA or anesthesiologist of record.

5.7.1 Return or Destruction of Study Drug

- As per current Mayo practice.

6 Study Procedures

Patient randomized to B12a or placebo. Data will be measured prospectively for the first 30 minutes and then taken from the EMR after that. All tests besides vitamin B12 assay and heavy metal quant will be done as standard of care and data will only be collected if done as standard of care. Vitamin B12 assay and heavy metal quant will be collected at 24 hours (\pm 1 hour) and 72 hours (\pm 1 hour) after drug administration.

Study Activity	Day 0	Day 1	Day 2	Day 3	Day 4	Day 5	Day 6	Day 7	30 Day F/U
Study Drug	X	X (window -1, -0)							
Informed consent	X	X							
History	X	X							
Concurrent meds	X	X							
Physical exam (Ht, Wt, VS)	X	X							
Patient monitoring for inclusion	X	X							
Randomization Res Pharm	X	X							
CBC w/diff, plts	X	X	X	X	X	X	X	X	
Serum chemistry ^a	X	X	X	X	X	X	X	X	
INR/PTT/Fib/Plt	X	X	X	X	X	X	X	X	
ABG/Lactate ^b	X	X	X	X	X	X	X	X	
Vitamin B12 Assay ^c		X	X	X	X				
Heavy Metal Quant ^c		X	X	X	X				
Hemodynamic monitoring									
Patient Call for follow up on adverse events and mortality									X

a: Albumin, alkaline phosphatase, total bilirubin, BUN, calcium, chloride, glucose, LDH, phosphorus, potassium, total protein, SGOT [AST], SGPT [13], sodium, creatinine
b: PaO₂, PaCO₂, pH, bicarb, SpO₂, lactate, base deficit
c: Vitamin B12 assay, heavy metal quant to be collected at 24 hour (\pm 1 hour) and 72 hour (\pm 1 hour) after study drug administration

7 Statistical Plan

7.1 Sample Size Determination

Sample size

Power analysis using the results of our retrospective review revealed a study population of 50 patients randomized to either B12a or control would detect a mean arterial pressure (MAP) increase of 7.3mmHg with a power of 0.8 and a p value of 0.05. The expected event rate triggering randomization is between 10% and 20% based on both historical data from previous series and evaluation of the percentage of patients meeting inclusion criteria based on a random selection of patients after cardiac surgery at our institution [5, 14]. This will require consent of 1000 to 2000 patients in order to randomize 50 patients. Our institution performs approximately 3000 cardiac surgical cases requiring CPB per year meaning we would need to consent between 4% and 8% of our cardiac surgical volume over a 2 year study period.

Problems and Limitations

Several potential limitations exist with this study. Firstly there is still no universally accepted definition of VS in the literature. Therefore physiological variables chosen for inclusion will by necessity be arbitrary. We chose variables based on definitions used in previous reviews. Furthermore, previous work suggests NOS inhibitors may be most effective early in the disease process and may be less effective after prolonged refractory VS [5, 22]. Given this we decided intervention with the study drug should occur while vasoplegia is refractory but before intervention would be considered as a rescue and therefore infusion of norepinephrine equivalents of 0.1mcg/kg/min² for 30 min was considered appropriate.

7.2 Statistical Methods

Descriptive Statistics

The primary outcome is change in MAP from baseline over the first 4 hours postoperatively at 15 min increments post randomization. Randomized groups will be compared using analysis of covariance (ANCOVA), adjusting for baseline MAP prior to randomization. A p-value <0.05 is considered statistically significant.

Secondary outcomes will be compared by treatment arms without adjustment for multiple comparisons. Change in rates of vasopressor and inotropic infusions will be compared by

ANCOVA where the outcome is defined as the infusion rate at 30 minute intervals for the first 4 hours post B12a administration and models adjust for the baseline value. Change in systolic blood pressure will be analyzed similarly. Length of stay and ventilator time outcomes will be compared by Wilcoxon rank-sum tests; mortality and binary outcomes will be compared between randomized arms with a Pearson chi-square or Fisher's exact test when appropriate.

As a tertiary aim and exploratory analysis, longitudinally collected data such as daily SOFA score will be modeled in a repeated measures analysis. Treatment groups will be compared by assessing whether B12 treatment affects the slope of or change in SOFA scores over time.

Handling of Missing Data

Missing data is expected to be rare as these outcomes are routinely collected in the electronic medical record. The primary analysis will consider complete cases. Two sensitivity analyses may be performed, including multiple imputation of missing data under the missing at random mechanism and an analysis under the not missing at random mechanism. For the latter, methods may include shared parameter models or worst-case imputation when the cause of the missing data is early mortality

Primary Hypothesis:

The use of an intravenous infusion of vitamin B12a in patients with post-cardiotomy vasoplegic syndrome receiving high dose vasopressors will result in a statistically significant increase in mean arterial blood pressure compared to placebo over the first 4 hours after administration.

Secondary Hypothesis:

The use of an intravenous infusion of vitamin B12a in patients with post-cardiotomy vasoplegic syndrome will have a statistically significant decrease in vasopressor requirement over the first 4 hours after administration.

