3.7 Identification of Source Data

The following source data will be directly recorded on the Case Report Form (CRF):

- Vital signs (T0 \pm 30 min, T0 represents time of drug administration)
 - Cardiac index

- MAP
 - SBP
 - Systolic Pulmonary Blood Pressure
 - Right Atrial Pressure
- Vasopressor infusion rates (T0±30 min, T0 represents time of drug administration)
 - Norepinephrine mcg/kg/min
 - Epinephrine mcg/kg/min
 - Vasopressin unit/min
 - Calcium mg/hour
 - Dopamine mcg/kg/min

The following source data will be directly collected in the Case Report Form (CRF), if we are not able to capture the data in the CRF due to limitations, it will be captured retrospectively in supportive documentation (study source documents, EMR):

- Laboratory tests will be taken as is standard in this patient population with no added tests specific for the study. Results and clinical interpretation will be via the EMR
 - Creatinine, ABG (FiO₂, PaO₂, PaCO₂, pH, Bicarb, Base Deficit, methemoglobin percentage), Lactate, INR, PTT, AST, ALT, Bilirubin, Hemoglobin, platelets
- Vitamin B12 assay and heavy metal quant results 24 hours and 72 hours after drug administration
- Urine output at each 24 hours.
- Vital signs
- Cardiac index at 15 min intervals from administration time T45 through the first 4 hours if the participant has a continuous pulmonary artery catheter. Cardiac index 30 minutes after administration time, times two, followed by every hour for 4 hours if the patient has a non-continuous pulmonary artery catheter and based upon the availability of the technician/therapist.
- MAP at 15 min intervals from administration time T45 through the first 4 hours
- SBP at 15 min intervals from administration time T45 through the first 4 hours
- Systolic Pulmonary Blood Pressure at 15 min intervals from administration time T45 through the first 4 hours
- Right Atrial Pressure at 15 min intervals from administration time T45 through the first 4 hours
- Hospital length of stay (LOS) (Days)
- ICU LOS (Days)
- Ventilator time (Hours)
- End organ dysfunction during the first seven days will not be directly collected in the CRF but will be captured retrospectively in supportive documentation:
 - Stroke (CT or MRI confirmed hemorrhagic or ischemic
 - AKI as defined by AKIN criteria
- New arrhythmias as diagnosed by in the EMR
- Need for mechanical circulatory support (LVAD, ECMO, Intra-aortic Balloon Pump, Impella)

4 Subject Selection Enrollment and Withdrawal

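### The primary MAP model omits baseline vasopressor dose, a covariate already collected: the analysis is valid, but it forgoes a probable gain in precision and protection against chance imbalance

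*Combined protocol and SAP*

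**What the plan says.** Section 7.2 defines the endpoint: "The primary outcome is change in MAP from baseline over the first 4 hours postoperatively at 15 min increments post randomization". The model is an ANCOVA with one covariate: "Randomized groups will be compared using analysis of covariance (ANCOVA), adjusting for baseline MAP prior to randomization". Baseline infusion rate is a covariate only in the secondary infusion-rate model. The sensitivity analyses in 7.2 concern missing data; none adds a covariate.

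Dose information is available. Section 3.7 lists among the CRF source data "Vasopressor infusion rates (T0±30 min, T0 represents time of drug administration", covering norepinephrine, epinephrine, vasopressin, calcium and dopamine. Entry under Table 1 of section 4.1 depends jointly on MAP (at most 75 mmHg) and on vasopressor support, one route being "Norepinephrine equivalent infusion of" at least 0.1 mcg/kg/min. No upper limit on dose is listed. Appendix Table 1 gives the conversion for four agents.

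Sections 5.3 and 5.4 assign randomization to the research pharmacy and describe no stratification.

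**The concern.** A MAP reading in these patients is the pressure reached on a given amount of support. Two patients with the same entry MAP can be on quite different norepinephrine-equivalent doses, because dose has a floor at entry and no stated ceiling. The primary model treats them as alike. If dose predicts later MAP beyond what baseline MAP predicts, that variation stays in the error term of the only test for which power is given. With a total of 50 patients, the arms could also differ in dose by chance, and the model would not correct for it. Adding the covariate only after an imbalance has been seen would be post hoc, so the choice has to be made in advance.

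**Working it through.** **Inputs from the documents (7.1, 7.2).** Total N comes from "a study population of 50 patients randomized to either B12a or control". Effect and power: "would detect a mean arterial pressure (MAP) increase of 7.3mmHg with a power of 0.8 and a p value of 0.05". Significance level: "A p-value <0.05 is considered statistically significant".

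**Assumptions.** 1:1 allocation (25 per arm), a two-sided test, and one summary MAP change per patient (7.2 does not say how the 15-minute values are combined). The partial correlation r of baseline dose with the MAP outcome, given baseline MAP, is not in the documents; it is varied from 0 to 0.5.

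**1. The plan's own figure.** No SD is stated; its source is only described as "Power analysis using the results of our retrospective review". N = 50 therefore cannot be reproduced independently, but the SD it implies can be solved for.
- Normal approximation: SD = 7.3 / [(1.960 + 0.842) × √(2/25)] = 9.21 mmHg.
- t test, 48 df: power 0.80 needs a standardized difference of 0.8087, so SD = 7.3 / 0.8087 = 9.03 mmHg.
- A one-sided test would imply 10.4 mmHg by the normal approximation.

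The rest uses about 9.0 mmHg as the residual SD given baseline MAP.

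**2. Power with the second covariate.** Adding dose multiplies the residual SD by √(1 − r²). Each covariate also costs a degree of freedom and, through chance imbalance, inflates the variance of the treatment estimate by an expected factor of 1 + k/(47 − k) for k covariates. That is 1 + 1/46 for one and 1 + 2/45 for two. Power is then taken from the noncentral t distribution at 7.3 mmHg.

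| Model | r | Power |
|---|---|---|
| Baseline MAP only | – | 0.79 |
| MAP and dose | 0 | 0.78 |
| MAP and dose | 0.2 | 0.80 |
| MAP and dose | 0.3 | 0.82 |
| MAP and dose | 0.4 | 0.85 |
| MAP and dose | 0.5 | 0.89 |

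The two models have equal power at r of about 0.15. Below that, the second covariate costs up to about one power point.

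**3. Chance imbalance.** Under unrestricted allocation, the between-arm difference in mean dose has standard deviation √(2/25) = 0.283 dose SDs. The probability that it exceeds 0.5 SD in either direction is 2 × [1 − Φ(0.5/0.283)] = 0.077, about 8%.

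The resulting shift in the MAP difference is imbalance × r × SD. For an imbalance of 0.5 SD:
- r = 0.2: 0.5 × 0.2 × 9.02 = 0.9 mmHg
- r = 0.3: 0.5 × 0.3 × 9.02 = 1.4 mmHg
- r = 0.5: 0.5 × 0.5 × 9.02 = 2.3 mmHg

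**4. Type I error.** In 20,000 simulated null trials of 25 per arm, with baseline MAP and dose generated independently, the model without dose rejected in 5.0% (r = 0.3) and 4.9% (r = 0.5). Among only those trials with an imbalance above 0.5 SD, it rejected in about 9% and 15%, against about 5% with dose in the model.

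**The case against.** A prespecified ANCOVA on the outcome's own baseline is a valid and common choice, and randomization keeps its overall error rate at 5%. Choosing further covariates is optimization; cardiac index and lactate are recorded too. All of that stands.

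A reader might infer that precision is definitely lost, or that dose is the strongest marker of severity in these patients. The documents support neither. They give no correlation, and vasopressors may be titrated to a pressure goal (1.5, 8.4), which could hold MAP near target and make r small. They do not report the spread of entry doses either. Because treatment is meant to come before the rescue stage (7.1), doses might cluster near the threshold.

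A reader might also infer that an imbalance in dose passes in full into the estimated effect. It does not: it is scaled by r. The 8% figure further assumes unrestricted allocation, which the documents neither state nor exclude.

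Finally, the added covariate needs some definition. The CRF window of T0 ± 30 min includes readings after dosing, and a pre-infusion value could still fall after randomization, whereas 7.2 places baseline before it. Phenylephrine is named as an available agent (1.1) but is in neither the 3.7 list nor Appendix Table 1. These points shape the fix; they do not remove the reason for it.

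**Conclusion.** The point holds as a cheap improvement to a valid analysis. The omission is plain from 7.2. The size of the gain is uncertain because it rests on an assumed r: a loss of about one power point at r = 0, about one point gained at 0.2, about three at 0.3 and about nine at 0.5. The imbalance argument is conditional. It concerns the roughly one trial in twelve in which dose differs by more than 0.5 SD, where the shift could be a noticeable fraction of the 7.3 mmHg target (2.3/7.3, or about 31%, for a 0.5 SD imbalance at r = 0.5; 0.9/7.3, or about 12%, at r = 0.2). All figures assume 25 per arm, a two-sided test and an SD of about 9.0 mmHg solved from the plan. They do not show that the primary result would be biased on average or that its error rate is wrong.

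**What to change.** In 7.2, keep the MAP outcome as stated and prespecify, before unblinding, two covariates for the primary ANCOVA: baseline MAP and the log of norepinephrine-equivalent dose. Define the dose as the last value before randomization, so that it shares its baseline time with MAP. Report the MAP-only model as a sensitivity analysis.

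State how agents outside Appendix Table 1, such as phenylephrine, enter the equivalent dose.

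The cost is a few sentences in 7.2, one degree of freedom, and about one power point if dose turns out not to be prognostic. Eligibility checking already requires the support level over 30 minutes to be known, so little or no new data should be needed; the exception to check is any agent not on the 3.7 list.
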